A major concern is the possibility that topical microbicides or oral chemoprophylaxis could facilitate infections with or select for drug resistant HIV-1 in those who become infected, or are unknowingly already infected. The primary concern is that women who become infected while using topical or oral antiretroviral agents will undergo seroconversion with concomitant high levels of HIV-1 viral replication in the presence of antiretroviral monotherapy facilitating the emergence of resistance to the antiretroviral agent contained in the product. This is a particular concern with microbicides based on the use of a single antiviral drug such as tenofovir. Currently in North America and Western Europe, approximately 10% of all new infections are attributed to viruses that contain at least one drug resistance mutation but there are no data yet regarding the incidence of resistance among recipients of single or dual drug chemoprophylaxis or microbicides.^{iv} There is also the potential for selection of drug resistance in women who unknowingly are already HIV-infected. This may be less of a concern with respect to topically applied products with little or no systemic absorption, as the concentrations absorbed may be too low to select for resistance in systemically circulating virus. However, there may be an impact on the local genital tract viral population, which may be distinct from the systemic circulating virus.

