3.2. Secondary Objectives

- To characterize the trajectory of CD4+ T-cell counts after HIV-1 seroconversion among antiretroviral treatment naïve participants assigned to an active microbicide or chemoprophylactic agent compared to control participants.
- To compare the plasma HIV-1 RNA level six months after HIV-1 seroconversion among antiretroviral treatment naïve participants assigned to an active microbicide or chemoprophylactic agent compared to control participants.

- To evaluate the prevalence of HIV-1 drug resistance mutations in plasma and genital tract specimens after HIV-1 seroconversion among participants assigned to an active microbicidal or chemoprophylactic agent compared to control participants.
- To evaluate the virologic response to initiation of antiretroviral therapy among participants assigned to an active microbicidal or chemoprophylactic agent compared to control participants in microbicide trials and by study specific analysis (for larger trials including current and future trials).
 - The proportion with HIV-1 RNA less than 50 copies/mL six months, twelve months, and twenty-four months following initiation of antiretroviral therapy
- To describe the CD4+ T-cell response to initiation of antiretroviral therapy in participants after seroconversion in microbicide trials.
 - The CD4+ T-cell increase six months, twelve months, and twenty-four months following initiation of antiretroviral therapy
- To compare the HIV-1 drug resistance profile, among antiretroviral therapy recipients, at the time of virologic failure (HIV-1 RNA >200 copies/mL at or after six months of antiretroviral therapy) in participants assigned to an active microbicidal or chemoprophylactic agent compared to control in microbicide trials and by study specific analysis (for larger trials including current and future trials).
- To evaluate the prevalence and persistence of HIV drug resistance mutations in plasma and cervical lavage fluid using more sensitive methods (which may include modified ultrasensitive assays of plasma HIV RNA) in study specific subgroups of seroconverters.
- To describe HIV-1 related (WHO Stage II) and AIDS-defining (WHO Stage III and IV) clinical events and deaths (from any cause) occurring among seroconverters with and without antiretroviral therapy.
- To compare the rate of HIV disease progression among participants assigned to an active microbicidal or chemoprophylactic agent compared to control.

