10.2.2. Secondary Endpoints

Consistent with the secondary study objectives, the following secondary endpoints will be assessed:

- **Immunologic response. (CD4+ T cell count).** CD4⁺ T cell counts at Weeks 0 and 2, Months 1, 3, 6 and every 6 months thereafter. Time from seroconversion to immunologic failure will be compared between active microbicide and placebo/control groups. Immunologic failure is defined as two consecutive measurements of CD4+ T-cell count within or below the range of 200-250 cells/mm³, or the development of an AIDS defining illness.
- **Virologic and immunologic responses (CD4+ T-cell count) after initiation of ART.** CD4+ T-cell count and blood plasma HIV-1 RNA levels over time after initiation of ART. Time from initiation of ART to immunologic and virologic failure.
- **HIV-1 related and AIDS-defining events.** Occurrence and frequency of HIV-1 related and AIDS-defining events. Time from enrollment to time of first AIDS-defining event or death.
- **Sexual behavior, partnership status, and occurrence of social harms.** Sexual behavior over time following seroconversion at Months 0, 3, 12, and 24 months. Participants who enroll ≥3 months after seroconversion will be followed at 12 months and 24 months only.
- **HIV-1 genotypic mutations and drug resistant virus.** Prevalence of HIV-1 genotypic mutations over time and drug resistant HIV-1 virus in plasma and genital tract. Proportions of infected participants acquiring a drug resistant HIV-1 virus.

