10.3. Sample Size

Preliminary data from the University of Washington/Fred Hutchinson Cancer Research Center (UW/FHCRC) Primary Infection Clinic was used to estimate within and between person components of variance in individuals with early HIV-1 infection. These data are taken from 150 days to 2 years post infection and, therefore, should give reasonable estimates of the variability in viral load around the viral set point. The between person variance component is 0.52 (\log_{10} copies²/ml²) and the within person variance component is 0.096 (\log_{10} copies²/ml²).^{xv}

In the HPTN 035 trial we expect 192 seroconverters: 128 in the placebo gel and control groups and 64 in the PRO2000 and BufferGel groups assuming an effectiveness of 50% for both active microbicides. This breakdown between groups is conservative since the true effectiveness will most likely be lower. Effectiveness that is lower than 50% will slightly improve the power of this study since the numbers between the active microbicide and placebo/control groups would be more balanced.

However not all of these 192 will be available for the evaluation of the primary endpoint at one year after seroconversion since:

By the time this study is in the field, several participants will have seroconverted more than one year ago. We estimate this number to be around 20 such that we will have 172 eligible seroconverters for the evaluation of the primary objective.

Newly-infected women may have elected to terminate from the parent study and/or do not wish to enroll in this study and/or have been lost to follow-up in the parent study. Of the 172 eligible women, we estimate that 15% of the women eligible for this study will not enroll due to one of the above reasons.

We will target no more than 5% lost to follow-up per year.

Therefore we anticipate that 138 seroconverters (92 from the placebo and control groups and 46 from the active microbicide groups, assuming that the active microbicides reduce HIV acquisition by 50%) will be available for the evaluation of the primary objective one year after seroconversion. The following table gives the power to detect various differences in the viral set point between the active microbicide and placebo/control groups.

Table 7: Power Calculation for Primary Endpoint

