10.6.2. Data Analysis

Primary Analyses

Descriptive analyses of the seroconverters will include calculation of the mean and median viral load by active microbicide and placebo/control groups. A simple t-test can be used to compare log-transformed viral load levels between these two groups. However, caution must be exercised in the interpretation of any difference (or lack of difference) found. Although the overall active microbicide and placebo/control groups should be comparable at baseline (in the parent study) due to randomization, individuals who seroconvert in the active microbicide group may not be comparable to individuals who seroconvert in the placebo/control group. Approaches described by Gilbert et al, *Biometrics*, 2003 will be used for isolating the effect of an intervention on post-seroconversion outcomes.^{xvi} Furthermore, the primary analysis will be restricted to

seroconverters that have not initiated ART in the first 12 months after seroconversion.

Linear regression using the log-transformed viral load levels as the outcome and baseline or other covariates (e.g. CD4+ T-cell) will be used to compute adjusted differences between the active microbicide and placebo/control groups. The interpretation of these adjusted differences is subject to the same cautions noted above.

Sub-group exploratory analyses will be performed to explore difference between type of products and type of controls. Mainly, seroconverters will be grouped by the type of intervention received: (1) PRO2000, (2) BufferGel, (3) Placebo gel, and (4) Condom only.

Secondary Analyses

Secondary analyses of CD4+ T-cell counts will be virtually identical to those described for viral load levels above, although it is typically not necessary to log-transform CD4+ T-cell levels to obtain valid inferences. Descriptive statistics will be used to characterize overall CD4+ T-cell levels and levels within subgroups. T-tests and linear regression will be used to obtain unadjusted and adjusted estimates of the treatment effect. Again, the interpretation of these differences is subject to the same cautions noted above for the primary analyses.

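### Resistance is compared between arms only as a share of infected women, a denominator the product itself can change, and the plan's selection caution is not carried over to it

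*Protocol*

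**What the plan says.** Section 10.2.2 lists, among the secondary endpoints, the prevalence of genotypic mutations over time and "Proportions of infected participants acquiring a drug resistant HIV-1 virus". Section 3.2 states the matching objective as a comparison with control of the "prevalence of HIV-1 drug resistance mutations in plasma and genital tract specimens after HIV-1 seroconversion among participants assigned to an active" product. For categorical endpoints assessed repeatedly, section 10.6.2 names Fisher's exact test at selected time points, with GEE as the more general method. Nowhere does the protocol compare resistant infections on the parent trial's randomised denominator.

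Section 2.1 gives the motivation: products "could facilitate infections with or select for drug resistant HIV-1 in those who become infected". That sentence covers two mechanisms, facilitating infection with resistant virus and selecting for resistance once a woman is infected.

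Under primary analyses, section 10.6.2 recognises that "individuals who seroconvert in the active microbicide group may not be comparable to individuals who seroconvert in the placebo/control group" and cites a sensitivity-analysis method for post-seroconversion outcomes. It repeats the caution for CD4+ counts. The text on the remaining secondary endpoints, which include resistance, does not.

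Section 10.3 plans on "128 in the placebo gel and control groups and 64 in the PRO2000 and BufferGel groups", "assuming an effectiveness of 50% for both active microbicides".

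**The concern.** A share among the infected has a numerator (resistant infections) and a denominator (all infections), and the product can move both. The share rises if resistant infections increase, and also if wild-type infections fall while resistant ones stay the same. In the other direction, a product that raised wild-type and resistant infections by the same factor would leave the share unchanged.

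So an arm difference in this endpoint cannot by itself answer the first question in section 2.1, whether a product facilitates resistant infection. The risk is that a difference produced by prevention is reported as a resistance harm. The endpoint is a legitimate description of seroconverters. The difficulty lies in reading its arm difference as a product effect.

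**Working it through.** **Inputs**
- Infections: 128 control and 64 active (10.3). Since 128 × (1 − 0.50) = 64 and 128 + 64 = 192, the plan's figures reproduce and imply equal numbers randomised to the two pooled groups.
- Evaluable at 12 months: 172 × 0.85 × 0.95 = 138.9. The protocol gives 138, split 92 and 46.
- After 15% non-enrolment alone: 128 × 0.85 = 108.8 and 64 × 0.85 = 54.4, so about 109 and 54. The protocol applies its 15% to 172 eligible women; using it for all 192 is my simplification.
- Background resistant share p: section 2.1 says "approximately 10% of all new infections are attributed to viruses that contain at least one drug resistance mutation", but for North America and Western Europe. For these sites p is an assumption, shown from 2% to 15%.
- Scenario, assumed for illustration: equal numbers randomised, and the same number of resistant infections in both groups.

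**Overall effectiveness E.** The share is p in control and p/(1 − E) in active, so the ratio is 1/(1 − E):
- E = 20%: 1/0.8 = 1.25
- E = 30%: 1/0.7 = 1.43
- E = 50%: 1/0.5 = 2.00

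At p = 10% and E = 50%, there are 12.8 resistant infections in each group. Per infected woman: 12.8/128 = 10% against 12.8/64 = 20%, ratio 2.0. Per woman randomised: 12.8 against 12.8, ratio 1.0. At p = 5% the shares are 6.4/128 = 5% and 6.4/64 = 10%.

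**If the 50% applies to wild-type infection only**, the ratio is 1/[p + (1 − p)(1 − E)]:
- p = 2%: 1/0.51 = 1.96
- p = 5%: 1/0.525 = 1.90
- p = 10%: 1/0.55 = 1.82
- p = 15%: 1/0.575 = 1.74

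**Chance that Fisher's exact test (two-sided 0.05) is nominally significant in this scenario at E = 50%, by exact enumeration**

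| Control vs active share | 128/64 | 109/54 | 92/46 |
|---|---|---|---|
| 5% vs 10% | 22% | 19% | 17% |
| 10% vs 20% | 43% | 36% | 32% |
| 15% vs 30% | 64% | 58% | 49% |

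With equal shares of 5% or 10% the corresponding figure is about 3%.

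**How wide bounds for non-enrolment could be.** Take p = 5%, with enrolment unrelated to resistance among those observed: 6.4 × 0.85 = 5.44 resistant cases are seen in each group, and 19.2 control and 9.6 active seroconverters are unseen. Worst-case limits for the per-randomised ratio are 5.44/(5.44 + 19.2) = 0.22 and (5.44 + 9.6)/5.44 = 2.76.

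**The case against.** Four points can be made for the plan.

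*The scenario is not the protocol's.* A reader might infer that the endpoint will show a doubling of resistance at the protocol's own 50% effectiveness. The documents do not support that. The 50% is a planning value for PRO2000 and BufferGel, and section 10.3 itself expects actual effectiveness to be lower. The resistance concern in section 2.1 centres on antiretroviral products, with tenofovir as its example. Nothing says the two gels block wild-type virus and spare resistant virus; if a product blocks both equally, the ratio is 1.0. This stands, and it limits the figures to an illustration. The mechanism remains relevant, because the protocol foresees parent trials of antiretroviral products.

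*The denominator suits part of the question.* Section 2.1 calls emergence of resistance in women infected while using an antiretroviral product its primary concern, and a share among infected women addresses that. This also stands, and is why the endpoint should be kept.

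*The per-randomised count can hide harm.* Suppose a product halves all infections, leaving 64 infected with 3.2 background resistant cases, and then selects resistance in 3.2 more. The per-randomised comparison is 6.4 against 6.4, ratio 1.0, while the share is 10% against 5%. A reader might infer that the per-randomised count should replace or outrank the planned measure; this example shows why it should not.

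*Selection is not overlooked.* A reader might infer that the protocol is blind to it. It is not: the caution is explicit and the cited method is described in general terms. But both sit under primary analyses, only CD4+ receives the repeat, and the method would not supply the count per woman randomised. Fuller detail could appear in an analysis plan not shown here; the denominator, however, is fixed in the protocol.

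**Conclusion.** The point holds in a limited form. The protocol fixes infected women as the only denominator for an active-versus-control comparison of resistance and does not extend its own selection caution to it. Under an assumed product that spares resistant virus, the share is inflated by 1.43 at 30% and 2.0 at 50% overall effectiveness, or about 1.74 to 1.96 if the 50% refers to wild-type infection only and background resistance is 15% to 2%. The chance of a nominally significant result from this alone is about 43% (128/64) or 32% (92/46) at 10% against 20%, and about 22% or 17% at 5% against 10%. All of these rest on the assumed mechanism and background share.

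Neither measure alone separates prevention of wild-type infection from product-selected resistance. The two should be read together, and even the pair does not always settle the mechanism: the halving-plus-selection example and the wild-type-only scenario give the same figures on both. What the companion adds is a direct answer on whether more women per arm end up with resistant virus. I would class this as a cheap improvement, not a defect that undermines the study.

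**What to change.** - In 10.2.2, keep the proportion among infected women as the measure bearing on selection of resistance after infection.
- In 10.6.2, state that the non-comparability caution given for viral load and CD4+ also applies to the resistance comparison.
- Add a companion comparison: women with resistant virus per woman randomised (or per person-year), by parent-trial arm and stratified by parent trial, with bounds for the roughly 15% of eligible seroconverters who do not enrol.
- State that the two measures will be interpreted together and that neither alone identifies the mechanism.

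The cost is a few sentences, parent-trial denominators and some extra analysis; no visit, procedure or specimen changes. The drawback is the assumption needed for women who do not enrol. With few resistant cases, worst-case bounds will be wide, so a narrower range with its assumption stated should be shown beside them.

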10.3. Sample Size

Preliminary data from the University of Washington/Fred Hutchinson Cancer Research Center (UW/FHCRC) Primary Infection Clinic was used to estimate within and between person components of variance in individuals with early HIV-1 infection. These data are taken from 150 days to 2 years post infection and, therefore, should give reasonable estimates of the variability in viral load around the viral set point. The between person variance component is 0.52 (\log_{10} copies²/ml²) and the within person variance component is 0.096 (\log_{10} copies²/ml²).^{xv}

In the HPTN 035 trial we expect 192 seroconverters: 128 in the placebo gel and control groups and 64 in the PRO2000 and BufferGel groups assuming an effectiveness of 50% for both active microbicides. This breakdown between groups is conservative since the true effectiveness will most likely be lower. Effectiveness that is lower than 50% will slightly improve the power of this study since the numbers between the active microbicide and placebo/control groups would be more balanced.

However not all of these 192 will be available for the evaluation of the primary endpoint at one year after seroconversion since:

By the time this study is in the field, several participants will have seroconverted more than one year ago. We estimate this number to be around 20 such that we will have 172 eligible seroconverters for the evaluation of the primary objective.

Newly-infected women may have elected to terminate from the parent study and/or do not wish to enroll in this study and/or have been lost to follow-up in the parent study. Of the 172 eligible women, we estimate that 15% of the women eligible for this study will not enroll due to one of the above reasons.

We will target no more than 5% lost to follow-up per year.

Therefore we anticipate that 138 seroconverters (92 from the placebo and control groups and 46 from the active microbicide groups, assuming that the active microbicides reduce HIV acquisition by 50%) will be available for the evaluation of the primary objective one year after seroconversion. The following table gives the power to detect various differences in the viral set point between the active microbicide and placebo/control groups.

Table 7: Power Calculation for Primary Endpoint

Power to detect the indicated difference in log ₁₀ HIV RNA (viral set point) between active microbicide and placebo/control groups assuming 46 and 92 individuals in those groups, respectively. The two-sided α level is 0.05.			
	Difference in log ₁₀ plasma HIV RNA (viral set point) at 12 months between active microbicide and placebo/control groups		
No. obs/person	0.3	0.4	0.5
1	56%	80%	94%
2	59%	83%	96%
3	61%	84%	96%
4	61%	85%	96%

Thus, we have 80% power to detect a difference of 0.4 log₁₀ copies/ml in viral set point at one year. This difference is comparable to what might be expected with nucleoside monotherapy and the minimum change in viral load that could have a measurable effect on HIV-1 disease progression. Due to the relatively low within-person variation in viral load, multiple measurements on an individual do not produce a significant increase in power. As mentioned above, if the effectiveness of the active microbicides is smaller than 50% then the power in this study would slightly increase since the numbers between the comparison groups would be more balanced.

From the available data and a poll of the site investigators currently conducting HPTN 035, we believe the number of women initiating ART in the first 6-12 months after seroconversion will be very low, less than 10%. Given that the primary analysis will be restricted to seroconverters that have not initiated ART in the first 12 months of seroconversion, the power of the study will decrease slightly. Assuming that 10% of seroconverters will initiate ART within the first 12 months, the study will have at least 76% power to detect a difference of 0.4 log₁₀ copies/ml in viral set point at one year.

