7.2. Follow-up Visits

This study utilizes two follow-up visit schedules, one based on the date of identification of seroconversion in the parent study and one based on initiation of ART use.

- Participants who have not initiated use of ART at the time of enrollment in MTN-015 will follow the schedule based on the date of identification of seroconversion, which is described in Section 7.2.1. On this schedule, follow-up visits occur at Months 1, 3, and 6 after the date of identification of seroconversion, and every 6 months thereafter. Participants may enroll anytime after seroconversion. Following the enrollment visit, the subsequent visits will be scheduled according to the seroconversion date (for example, a participant who enrolls 4 months after seroconversion would have a second visit at 6 months after seroconversion (2 months after enrollment) and then every 6 months).
- Participants who have initiated use of ART at the time of enrollment in MTN-015 will follow the schedule based on the date of ART initiation, which is described in Section 7.2.2. On this schedule, follow-up visits occur at Week 2 and Months 1, 3, and 6 after the date of ART initiation, and every 6 months thereafter.
- Participants who initiate use of ART during follow-up in MTN-015 will follow the schedule in section 7.2.1, and then switch to the schedule in Section 7.2.2 after initiation of ART use.

As it will not always be possible to conduct follow-up visits on the target dates specified above, visits may be completed at any time during allowable visit windows. For both the non-ART and ART visit schedules, the allowable visit windows are contiguous and extend from the midpoint of one visit interval to the midpoint of the next visit interval. For example, the Month 24 visit window extends from Month 21 through Month 27. For participants who do not complete scheduled visits within the allowable window, the visit will be considered missed and relevant case report forms will be completed to document the missed visit. Missed visits will not be considered protocol violations.

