10.5. Participant Accrual and Retention

All seroconverters, regardless of their seroconversion date, from the ongoing HPTN 035 and 059 trials will be recruited into this study. Although some of these participants would have seroconverted more than a year ago, which would make them ineligible for the primary objective of this study, those participants could be used in the assessment of some of the secondary objectives. All newly identified seroconverters during follow-up in HPTN 035 and 059 will be recruited for this study.

Once a participant has enrolled in the study, the study site will make every reasonable effort to retain her for the entire study period. A maximum of 5% annual loss-to-follow-up of enrolled participants is targeted.

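### The primary analysis excludes women by whether ART began before Month 12, not before the sample used, and nothing in the plan addresses the selection this can cause

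*Protocol*

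**What the plan says.** The primary objective (Protocol 3.1) compares plasma HIV-1 RNA at twelve months between active and control participants who are ART-naïve. Section 10.2.1 makes the 12-month value the endpoint, and 10.6.2 names a t-test on log viral load.

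The exclusion rule is in 10.3: "Given that the primary analysis will be restricted to seroconverters that have not initiated ART in the first 12 months of seroconversion", power falls slightly. The plan assumes that 10% start ART in that time and gives at least 76% power for 0.4 log10, down from 80%. Section 10.6.2 states the same restriction.

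On visit timing, 7.2 says that "the allowable visit windows are contiguous and extend from the midpoint of one visit interval to the midpoint of the next visit interval". The non-ART visits around Month 12 are Months 6 and 18, so the Month 12 window runs from Month 9 to Month 15.

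On repeated measures, 10.3 tabulates one to four observations per woman and concludes that "multiple measurements on an individual do not produce a significant increase in power".

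Section 9.1 returns laboratory results to the participant and her medical provider in real time. Section 13.3 lists, as a possible benefit, earlier treatment arising from the monitoring of CD4+ counts and plasma HIV-1 RNA. The study hypothesis (2.2.1) is that study agents have no impact.

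**The concern.** There are two linked problems.

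**Selection.** Starting ART happens after infection and may be prompted by the quantity being compared. If women with higher viral load are more likely to start, the arm with the higher set point loses more of its upper tail. The women who remain then differ less than all seroconverters do. A product that raises set point looks less harmful, and one that lowers it looks less beneficial. Section 10.6.2 warns that seroconverters in the two arms may not be comparable and plans a published sensitivity approach for that. It has no matching caution or method for this second selection. Section 10.3 treats the exclusion as a loss of sample size only.

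**Timing.** Exclusion depends on ART before Month 12, but the sample may be drawn at any time from Month 9 to Month 15. A woman sampled untreated at Month 10 who starts ART at Month 11 is excluded although her sample is valid. In the other direction, the rule does not itself exclude a woman who starts ART after Month 12 but before she is sampled in the window.

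Section 10.3 describes 0.4 log10 as the minimum change that could measurably affect progression, so shrinkage below it matters.

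**Working it through.** **Inputs from Protocol 10.3.** "The two-sided α level is 0.05"; power is calculated "assuming 46 and 92 individuals in those groups, respectively" (active, then placebo/control); "The between person variance component is 0.52" and "the within person variance component is 0.096" on the log10 scale; 10% start ART within 12 months.

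**The plan's own figures.**
- Women available: 172 × 0.85 × 0.95 = 138.9 (stated 138).
- SD for one observation: √(0.52 + 0.096) = 0.785.
- SE with 46 and 92 women: 0.785 × √(1/46 + 1/92) = 0.142. Then 0.4/0.142 = 2.82, and power = Φ(2.82 − 1.96) = 80.6% (stated 80%).
- With 10% removed at random (41.4 and 82.8): SE = 0.149, 0.4/0.149 = 2.68, power = Φ(2.68 − 1.96) = 76.3% (stated 76%).

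All twelve cells of Table 7 reproduce within one point. The 76% changes only the sample size and leaves the difference at 0.4, so it holds only if ART start is unrelated to viral load.

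**If ART start depends on viral load.** The documents give no strength for the link, so it is assumed and varied. Large cohorts were simulated with the plan's variance components, one third of women in the active arm and a true difference of 0.4. ART start depended on Month 6 viral load in the same way in both arms. The last row lets exactly the women with the highest 10% of values start. Each cell gives the observed difference and the power.

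| Link (odds ratio per log10), 10% starting | Product raises viral load | Product lowers viral load |
|---|---|---|
| 1 (none) | 0.40, 76% | 0.40, 76% |
| 2 | 0.39, 75% | 0.39, 75.5% |
| 3 | 0.38, 74% | 0.38, 75% |
| 5 | 0.37, 72% | 0.37, 74% |
| 10 | 0.35, 69% | 0.355, 72% |
| Strict threshold | 0.30, 61% | 0.315, 67% |

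One cell worked through (product lowers viral load, odds ratio 10): 11.9% of control and 6.2% of active women start. That leaves 92 × 0.881 = 81.1 and 46 × 0.938 = 43.1 women, with SD 0.743. SE = 0.743 × √(1/81.1 + 1/43.1) = 0.140; 0.355/0.140 = 2.54; power = Φ(2.54 − 1.96) = 72%. Simulation error and the choice of pooled or arm-specific SD can move power by one or two points.

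With 5% starting and odds ratios of 2 to 10, the difference is about 0.40 to 0.37 and power about 78% to 74%. With a true difference of zero, no scenario run showed bias.

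**What pre-ART values recover.** Using each starter's last pre-ART value gives back 0.40 to 0.42 in these scenarios. For power within the planned 138 women, let non-starters contribute Months 6 and 12, and let a fraction f of starters contribute one pre-ART Month 6 value. Information per woman is 0.9/(0.52 + 0.096/2) + 0.1f/0.616:
- f = 0: 1.585, variance 0.631, power 79.6%
- f = 0.5: power 81.6%
- f = 1: 1.747, variance 0.572, power 83.3%

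This assumes the same arm difference at Months 6 and 12.

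**The case against.** The restriction follows from an objective worded for ART-naïve women, and its cost in sample size is disclosed and correctly computed. The protocol expects fewer than 10% to start ART, and at 5% the graded losses are small. The link is plausible from 9.1 and 13.3 but not quantified: 9.1 refers women for care under local guidelines and names no viral-load criterion. All of this stands, and it makes the bias conditional.

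The use of one value per woman is also a reasoned choice. Table 7 shows the modest gain from more, and six-month viral load has its own secondary objective. Replacing the endpoint with a model over Months 6 to 24 would change what is estimated.

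A reader might infer three stronger points that the documents do not support.
- **That on-treatment values will enter the primary comparison.** The objective is limited to ART-naïve women, and 4.1 and 7.2 move those who start ART to a separate schedule, so a post-ART Week 2 visit is not the post-seroconversion Month 12 visit. The fair statement is only that the Month 12 cut-off does not itself rule such a value out.
- **That about 88% power is being given up.** That needs 192 × 0.85 × 0.95 = 155 women with two or three values each, although women who start ART early would often have one value or none.
- **That the roughly 20 women seroconverting more than a year earlier are wrongly set aside** (10.5: "which would make them ineligible for the primary objective of this study"). Only those sampled by Month 15 fit the window; leaving out the rest follows from a 12-month endpoint.

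What the objection does not answer is that 10.6.2 covers only selection into seroconversion, and that the cut-off does not match the sample window.

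**Conclusion.** The point holds in a conditional form and is worth changing. The rule ties inclusion to a calendar cut-off rather than to treatment status at sampling, so it can discard valid untreated samples from Months 9 to 12. It can also select on the outcome, with no analysis planned to show by how much.

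At 10% starting, the understatement of a true 0.4 is about 0.01 to 0.05 log10 for a graded link and about 0.10 at the strict threshold, which is an outer bound. Power is then about 75% to 69%, or 61% at that bound, against the stated 76%. These sizes rest on an assumed link that acts alike in both arms. A reader might take the bias as established. It is not: it vanishes if ART start is unrelated to viral load or if the true difference is zero, so no false signal arises. The stated 80% and 76% contain no arithmetic error.

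**What to change.** In 10.6.2:
- Define ART-naïve by whether ART began before the sample used. Any pre-ART sample inside the Month 12 window is kept, and no on-ART sample counts.
- Keep the 12-month endpoint.
- Add a pre-specified analysis that includes women who start ART through their pre-ART viral loads. This can use the last pre-ART set-point value from Month 6 on, or a mixed model of pre-ART values estimating the Month 12 difference. Report it beside the restricted comparison.
- Extend the existing caution to selection on ART start.

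In 10.3, state that 76% assumes ART start is unrelated to viral load.

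The cost is analysis wording and a little more analysis; the viral loads are already scheduled. The added assumption is that the Month 6 value reflects set point, which fits the plan's use of variance data from 150 days to 2 years. Within the planned 138 women, a model using Months 6 and 12 would raise power from about 76% to between 80% and 83%, depending on how many starters have a pre-ART Month 6 value.
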